8.5. Early Termination

Subjects who withdraw early should complete Study Exit procedures described in [Section 8.4](#).

8.6. Blood Volume

Safety blood draws: Approximately 20 mL of blood will be drawn at each study visit for a combined total of 80 mL.

9. TREATMENT OF SUBJECTS

9.1. Description of Study Drug

Study drugs will be provided by Impax for this study:

IPX203 (carbidopa-levodopa) Extended-Release Capsules, in four strengths, containing 35-140 mg, 52.5-210 mg, 70-280 mg, and 87.5-350 mg of CD-LD, for oral administration.

Table 3: Study Drugs for Study IPX203-B16-03

Investigational Product	Dosage Form and Strength (mg CD-LD)	Manufacturer
IPX203 (carbidopa-levodopa) Extended-Release Capsules	35-140 mg capsule 52.5-210 mg capsule 70-280 mg capsule 87.5-350 mg capsule	Impax Laboratories, LLC

9.2. Concomitant Medications

9.2.1. Permitted PD Medications and Surgical Treatments

Concomitant therapy with amantadine, selective monoamine oxidase (MAO) type B inhibitors (eg, safinamide, selegiline, rasagiline), anticholinergic PD medications (eg, benztrapine, trihexyphenidyl), hypnotics (including low doses of quetiapine ≤ 25 mg per day), dopamine agonists, including apomorphine, supplemental CD, and COMT inhibitors are allowed provided the doses and regimens (and any adjustments) are recorded on the concomitant medication form. Implantation of a deep brain stimulator (DBS) for the treatment of PD is permitted during this study provided the stimulation settings are recorded.

Although apomorphine, supplemental CD, COMT inhibitors, and DBS were not permitted in Study IPX203-B16-02, these treatments may be initiated during the current study.

All concomitant medications taken during this study will be recorded.

9.2.2. Prohibited PD Medications and Surgical Treatments

Prohibited treatments during the study include the following:

- Any doses of Rytary and Duopa during this study.
- Nonselective MAO inhibitors or selective MAO type A inhibitors (MAO-A).
- Neurosurgical ablation treatment procedures for PD.
- Investigational agents other than IPX203.
- Dopamine antagonists with the exception of low doses (≤ 25 mg) of quetiapine for sleep.

A subject who reports the use of any prohibited medications will be discontinued.

9.3. Treatment Compliance

Study drug accountability and reconciliation will be performed by the site staff and the study monitor.

9.4. Randomization and Blinding

This is a nonrandomized open-label study.

10. STUDY DRUG MATERIALS AND MANAGEMENT

10.1. Study Drug

The study drug is IPX203 (carbidopa-levodopa) Extended-Release capsules for oral administration, provided in 4 dose strengths:

- IPX203 35-140 mg CD-LD capsule
- IPX203 52.5-210 mg CD-LD capsule
- IPX203 70-280 mg CD-LD capsule
- IPX203 87.5-350 mg CD-LD capsule.

IPX203 will be supplied by Impax.

10.2. Study Drug Packaging and Labeling

Impax or designee will provide study medications in bottles with appropriate labeling affixed.

Labels on the study medication may include the following information:

- Name, address, and phone number of the Sponsor.
- Pharmaceutical dosage form/route of administration, quantity of dosage units, the name/identifier, and strength/potency.
- Batch and/or code number to identify the contents and packaging operation.
- Trial reference code (protocol number).
- Trial subject identification number and where relevant, the visit number.
- Name of Investigator.
- Directions for use: Take capsule(s) orally with water as directed.
- For clinical trial use only.
- Storage information: Store at room temperature between 15-30°C (59-86°F).
- Protect from light and moisture.
- Period of use (use-by date, expiry date or retest date as applicable), in month/year format and in a manner that avoids any ambiguity.
- Keep out of reach of children.
- Caution statement: Caution: New Drug—Limited by Federal (or United States) law to investigational use.

10.3. Study Drug Storage

The study medications should be stored at 25°C (77°F), with excursions permitted to 15°C to 30°C (59°F to 86°F). They should be stored in a tightly closed container, protected from light

and moisture. Storage temperature excursions below 15°C (59°F) or above 30°C (86°F) should be reported to Product Development at Impax or its designee.

10.4. Study Drug Administration

Subjects will be instructed to take their medications with approximately 240 mL of room-temperature water. The capsules should not be crushed or chewed.

10.5. Study Drug Dispensing and Accountability

The Investigator must ensure that all study medication received at the study site is inventoried and accounted for, and that dispensed study medication is recorded in the subject's source documents, the CRF, and the study medication inventory log. Site personnel must not relabel or reassign study medication to other subjects or to individuals not enrolled in the study. The study monitor verifies medication accountability during monitoring visits.

10.6. Study Drug Handling and Disposal

The Investigator must retain and properly store all partially used and unused study medication until authorized by Impax regarding disposition.

11. ASSESSMENT OF EFFICACY

To allow for assessment of the sustainability of the clinical effect of IPX203 over the 9-month study duration, the following clinical utility measures will be assessed at every visit: PGI-S, CGI-S, TSA, PDSS-2, PDQ-39, PAS, NMSS, MDS-UPDRS Parts I to IV, ZBI-12 and EMSQ.

11.1. Patient and Investigator Global Assessments

- Patient Global Impression of Severity (PGI-S) ([Appendix E](#)): The subject will determine the severity of the disease on a 7-point scale ranging from “Normal, not at all ill” (1) to “Extremely severely ill” (7) at the time of the assessment.
- Clinical Global Impression of Severity (CGI-S) ([Appendix F](#)): The clinician will determine the severity of the disease on a 7-point scale ranging from “Normal, not at all ill” (1) to “Among the most extremely ill of subjects” (7) at the time of the assessment.

11.2. Treatment Satisfaction Assessment (TSA)

The TSA is a single-question, self-reported questionnaire ([Appendix L](#)). The subject will determine his/her treatment satisfaction using a 7-point scale ranging from “Very much dissatisfied” (1) to “Very much satisfied” (7) at the time of the assessment.

11.3. Parkinson’s Disease Sleep Scale-2 (PDSS-2)

The PDSS-2 is 15-item self-reported questionnaire ([Appendix J](#)). Three domains are defined: disturbed sleep (Questions 1-3, 8, 14), motor symptoms at night (Questions 4-6, 12, 13), PD symptoms at night (Questions 7, 9-11, 15).

11.4. Parkinson’s Disease Questionnaire-39 (PDQ-39)

The PDQ-39 is a self-reported questionnaire ([Appendix G](#)). Using the 39 items, 8 domains are defined: mobility (Questions 1-10), activities of daily living (ADL) (Questions 11-16), emotional well-being (Questions 17-22), stigma (Questions 23-26), social support (Questions 27-29), cognition (Questions 30-33), communication (Questions 34-36) and bodily discomfort (Questions 37-39).

11.5. Parkinson Anxiety Scale (PAS)

The PAS is a 12-item subject- or observer-rated questionnaire with 3 domains: persistent anxiety (Questions A.1-A.5), episodic anxiety (Questions B.1-B.4) and avoidance anxiety (Questions C.1-C.3) ([Appendix K](#)).

11.6. Non-Motor Symptom Assessment Scale for Parkinson’s Disease (NMSS)

The NMSS is a 30-item, investigator-rated questionnaire ([Appendix I](#)). The NMSS contains 9 domains: cardiovascular (Questions 1, 2), sleep/fatigue (Questions 3-6), mood/cognition

(Questions 7-12), perceptual problems (Questions 13-15), attention/memory (Questions 16-18), gastrointestinal (Questions 19-21), urinary (Questions 22-24), sexual function (Questions 25, 26), and miscellaneous (Questions 27-30).

11.7. Movement Disorders Society Version of Unified Parkinson's Disease Rating Scale (MDS-UPDRS)

The MDS-UPDRS has 4 parts ([Appendix D](#)):

- Part I: Non-Motor Aspects of Experiences of Daily Living (nM-EDL) has 2 components. Component IA contains a number of behaviors assessed by the investigator with all pertinent information from the subjects and caregivers. Component IB is completed by the subject with or without help from the caregiver but independent of the investigator. These sections can be reviewed by the rater to ensure all questions are answered clearly and the rater can help explain any ambiguities.
- Part II: Motor Aspects of Experiences of Daily Living (M-EDL) is a self-administered questionnaire but can be reviewed by the investigator to ensure completeness and clarity.
- Part III: Motor Examination assesses the motor signs of PD and has instructions for the rater to give to or to demonstrate to the subject. It is completed by the rater.
- Part IV: Motor Complications integrates subject-derived information with the rater's clinical observations and judgements and is completed by the rater. It contains instructions for the rater and instructions to be read to the subject.

11.8. 12-Item Zarit Burden Interview (ZBI-12)

The Zarit Burden Interview (ZBI) is used to assess the perceived burden of family caregivers who provide assistance to patients with long-term progressive neurological disorders, including PD. The ZBI-22 consists of 22 items with five ordered frequency-related response categories scored 0 (never) to 4 (nearly always), except for the final item, which has 5 ordered intensity-related response categories (0 = not at all; 4 = extremely). All 22 items are used to calculate a total score that can range between 0 and 88 (88 = more burden). A total score of 21 has been suggested as a burden cut point. The ZBI-12 is a 12-item short form of the ZBI-22 and has been shown to be reliable and valid and to produce results that are similar to the longer version ([Hagell et al 2017, Bédard et al 2001](#)) ([Appendix M](#)) while minimizing respondent time and burden. The ZBI-12 should be completed by the same caregiver during each visit.

11.9. Early Morning Symptom Questionnaire (EMSQ)

The EMSQ is a 3-question, subject-rated questionnaire ([Appendix N](#)) that is used to assess whether a subject is experiencing any of 10 early morning PD symptoms by answering questions about prevalence (Question 1), severity (Question 2), and response to the first morning dose of PD medications (Question 3). Study site staff will complete this questionnaire by questioning subjects during each study visit.

12. ASSESSMENT OF SAFETY

12.1. Safety Parameters

Safety will be assessed by the following parameters:

- Electrocardiograms (ECGs), clinical laboratory tests, physical examinations, the Columbia-Suicide Severity Rating Scale (C-SSRS), and vital signs, including supine and standing orthostatic blood pressure and heart rate.
- Adverse events and concomitant medications will be evaluated throughout the course of the study.
- The Gastroparesis Cardinal Symptom Index (GCSI) at Screening, and Visit 4 (Exit) only.

12.2. Adverse Events

12.2.1. Definition of Adverse Event

An adverse event (adverse experience) is any untoward medical occurrence in a patient or clinical trial subject administered a medicinal product and which does not necessarily have to have a causal relationship with this treatment. An adverse event can therefore be any unfavorable and unintended sign (eg, an abnormal laboratory finding), symptom, or disease temporally associated with the use of a medicinal product, whether or not considered related to the medicinal product.

All AEs and any clinically significant physical examination findings, 12-lead ECG abnormalities, or clinical laboratory measurements occurring during the study that were not present prior to administration of study medication and that continue at Study Exit should be followed and evaluated with additional tests, if necessary, until the AEs are medically stable or resolved. Follow-up on these AEs should be recorded on the source documents and reported to Impax.

12.2.2. Recording Adverse Events

Elicit information about AEs with nonselective questions such as: “Have you experienced any changes in your health status since your last visit?” Encourage subjects to report AEs at onset.

Record information for any AE that emerges from the time the subject signs the ICF until Study Exit.

Monitor each subject closely for the development of AEs and record all such events on the AE page of the CRF. Whenever possible, group signs and symptoms that constitutes a single diagnosis. For example, cough, rhinitis, and sneezing might be grouped as upper respiratory infection.

For each AE, record the onset date, severity, seriousness, relationship to study medication, date of resolution (or continuing), action taken, and outcome in the CRF. The Investigator is to make a causality assessment (relationship to study medication) for every AE.

12.2.3. Follow-up

The Investigator must follow each AE until resolved or medically stable.

12.2.4. Relationship to Study Drug

The Investigator documents his/her opinion of the relationship of the AE to the study medication as follows:

- Not Related—the experience can be readily explained by the subject's underlying medical condition or concomitant medications and no relationship exists between the study medication and the experience.
- Unlikely Related—the temporal relationship between the AE and the administration of the study medication is uncertain and it is likely that the AE can be explained by the subject's medical condition or other therapies.
- Possibly Related—there is some logical temporal relationship between the AE and the administration of the study medication and the experience is unlikely to be explained by the subject's medical condition or other therapies.
- Related—the temporal relationship is compelling between the administration of the study medication and the AE cannot be explained by the subject's medical condition or other therapies.

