12.3.2. Reporting Serious Adverse Events

Any SAE that occurs from the time the subject signs an ICF until 30 days after taking the final dose of study medication must be reported by the investigative staff to the Sponsor or the Sponsor's representative within 24 hours of knowledge of the event (see [Study Contact Information](#)).

An SAE form must be completed and sent to the Sponsor and/or the Sponsor's representative. All SAEs must also be recorded on the AE page of the CRF. Additionally, all SAEs must be reported to the institutional review board (IRB) per the IRB's requirements.

Those SAEs that are considered both serious and unexpected and related to the study drug are subject to expedited reporting. An "unexpected AE" is any AE where the nature or severity is not consistent with the current investigator brochure (IB) or if an IB is not required or available, the specificity or severity is not consistent with the provided risk information.

Unexpected fatal or life-threatening SAEs related to the study drug must be reported by the Sponsor to the appropriate regulatory authority in an expedited manner (ie, first report within 7 days of first knowledge by the Sponsor). The Sponsor will provide a final written report to that authority within 15 days of initial receipt of information on the event. The Sponsor or the Sponsor's representative will also inform all participating Investigators of the SAE.

Unexpected SAEs that are not fatal or life-threatening must be reported by the Sponsor to the appropriate regulatory authority as soon as possible but no later than 15 calendar days after first knowledge of the SAE by the Sponsor. The Sponsor or the Sponsor's representative also informs all participating Investigators of the SAE.

Subjects withdrawn from the study due to any SAE will be followed until the SAE is resolved or medically stable. Record all SAEs, regardless of severity and whether or not related to the study medication, on the appropriate page of the CRF.

The Investigator must determine whether the seriousness of the event warrants removal of the subject from the study. He/she should, in any case, institute appropriate diagnostic and therapeutic measures and keep the subject under observation for as long as is medically indicated, or refer the subject to appropriate health professionals.

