13.6. Analysis of Safety

The safety analysis will include all subjects who received at least one dose of study medication. Adverse events, supine and standing orthostatic vital signs, concomitant medications, electrocardiograms (ECGs), clinical laboratory tests, physical examinations, and the Columbia-Suicide Severity Rating Scale (C-SSRS) will be evaluated throughout the course of the study.

Adverse events will be collected and summarized both for the time in the open-label extension trial and the time of overall IPX203 exposure. For summary and reporting purposes, “unlikely related,” “possibly related,” and “related” will be combined and will be counted as “related.”

Vital signs and ECGs will be summarized across the entire IPX203 exposure including information from the open-label extension and the prior IPX203-B16-02 study into which the subjects were enrolled.

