5.1 Adverse Events

Adverse Events will be coded using the Medical Dictionary of Regulatory Activities (MedDRA) version 22.0 AE coding system for purposes of summarization.

Only Treatment Emergent Adverse Events (TEAE) will be used for the summary analysis, unless otherwise specified. An AE will be considered as treatment-emergent if the date of onset is on or after the date of the first open-label study drug administration in the study IPX203-B16-03 and no later than 1 day after the last study drug dose in the study. AEs with unknown start dates will be counted as treatment-emergent unless the AE resolution date is prior to the first open-label study drug administration date. If the AE start date is partially missing, the AE will be considered treatment-emergent, unless the month and year (when available) rule out the possibility that the event occurred post start of the open-label study drug and no later than 1 day after the last study drug dose.

A TEAE is defined as treatment-related if it is recorded as “possibly related” or “related” to the study medication on the eCRF. AEs recorded as “not related” or “unlikely related” will be considered not related. In case the relatedness was not assessed, the most conservative result (related) will be chosen for the analysis.

In summaries of TEAEs a subject experiencing the same AE (with the same preferred term) multiple times will only be counted once for that preferred term. Similarly, if a subject experiences multiple AEs within the same system organ class, that subject will be counted only once in that system organ class. When summarizing AEs by severity, only the most severe occurrence within the preferred term or system organ class will be used. Similarly, when summarizing AEs by relationship to study drug, only the most related occurrence within the preferred term or system organ class will be selected for displays in summary tables.

An overall summary will include, by treatment group and overall, the number and percentage of subjects reporting at least 1 TEAE in the following categories:

- Any TEAE
- Treatment-related TEAE
- Serious TEAE
- TEAE leading to discontinuation of the study drug
- TEAE leading to death.

The following TEAE frequency tables will be prepared summarizing the overall number of TEAEs, the number and percentage of subjects reporting at least one TEAE by MedDRA System Organ Class (SOC) and preferred term (PT), by treatment group and overall:

- All TEAEs
- Serious TEAEs

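### The causality scale has no category for an AE with a logical time link and a competing explanation, and the protocol and SAP disagree on whether an AE coded unlikely counts as related

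*Protocol*

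**What the plan says.** Protocol 12.2.4 gives four levels. Each joins two conditions with the word and.

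- **Not Related:** the event is readily explained by underlying illness or "concomitant medications and no relationship exists between the study medication and the experience".
- **Unlikely Related** applies when "the temporal relationship between the AE and the administration of the study medication is uncertain and it is likely that the AE can be explained" in terms of illness or other treatment.
- **Possibly Related** applies when "there is some logical temporal relationship between the AE and the administration of the study medication and the experience is unlikely to be explained by" those same causes.
- **Related** applies when "the temporal relationship is compelling between the administration of the study medication and the AE cannot be explained by" those causes.

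Neither document says how to code an event that fits no level.

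SAP 5.1 sets the cut-off above the second level: "A TEAE is defined as treatment-related if it is recorded as" possibly related or related, and "AEs recorded as “not related” or “unlikely related” will be considered not related". Protocol 13.6 sets it one level lower: unlikely, possibly and related "will be combined and will be counted as" related. SAP section 7 lists the changes from the protocol's analyses. It does not mention this one, and it states that the safety analyses depart from the protocol in no other way.

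**The concern.** Every subject has advanced Parkinson's disease. Protocol 9.2.1 permits dopamine agonists, apomorphine, amantadine, MAO-B inhibitors and COMT inhibitors, and some of these may be started during the study. The trial's own disease scales score hallucinations, light-headedness on standing and dyskinesia. For the AEs of most interest with levodopa, a second explanation will therefore often be available even when the timing fits the study drug. The scale does not provide for that situation.

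The gap lies across the SAP's cut-off. Two investigators facing the same event can choose the levels on either side of it, and the treatment-related TEAE table would then partly reflect how each site reads the scale. The SAP takes the conservative value (related) when causality was not assessed, but gives no such protection to an event that was assessed on a scale that does not fit it.

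**Working it through.** The plan gives no figure to reproduce. The check is a logical enumeration followed by a sensitivity calculation.

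**1. Is there a gap?** Cross three strengths of time link with five strengths of the alternative explanation, and enter each level whose two conditions are both met (U = Unlikely, P = Possibly, R = Related). A compelling link is taken to be logical as well. Not Related is left out because it also requires that no relationship exists.

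| Time link | Alternative readily explains | likely explains | could explain | is unlikely to explain | cannot explain |
|---|---|---|---|---|---|
| Uncertain | U | U | none | none | none |
| Some logical | none | none | none | P | P |
| Compelling | none | none | none | P | P and R |

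The empty cells number 3 + 3 + 3 = 9 of 15. Six of them combine a logical or compelling link with an alternative that could, likely or readily explains the event. The other three have an uncertain link and no likely alternative.

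**2. Does the wording push these events downwards?** Count the failed conditions for an event with a logical link.

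- Alternative likely: Unlikely fails one condition (timing) and Possibly fails one (alternative), a tie.
- Alternative merely could explain it: Unlikely fails both conditions and Possibly fails one.

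The wording therefore does not favour Unlikely.

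**3. How do the two rules treat each level?**

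| Coded as | SAP 5.1 | Protocol 13.6 |
|---|---|---|
| Not Related | not related | not related |
| Unlikely Related | not related | related |
| Possibly Related | related | related |
| Related | related | related |

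The rules differ only for Unlikely. Under protocol 13.6 the choice between Unlikely and Possibly does not change the count. Under SAP 5.1 it does.

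**4. What could it amount to?** The number of subjects who are related under protocol 13.6 but not under SAP 5.1 because of gap events is D = N × p × g × u. Here N = 300 (protocol 6.2), p is the proportion with any TEAE, g the share of those whose only candidate related AE lies in the gap, and u the share of these coded Unlikely. The documents give none of p, g or u. I assume p from 30% to 60% and g from 10% to 40%.

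- u = 0: D = 0.
- u = 1, low end: 300 × 0.30 × 0.10 = 9 subjects; 9/300 = 3 percentage points.
- u = 1, high end: 300 × 0.60 × 0.40 = 72 subjects; 72/300 = 24 percentage points.

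Events properly coded Unlikely also differ between the two rules and are not included in D.

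**The case against.** A reader might infer that typical dopaminergic AEs slide to Unlikely, so that the treatment-related table is biased low. The documents do not support this. A gap event also fails Unlikely, because its timing is not uncertain. What evidence there is points the other way. In the single-dose study described in the protocol introduction, 6 of the 9 subjects with an AE (67%) had a related one, and these included every report of dizziness, nausea and dyskinesia. In the multiple-dose study, 8 subjects had a related AE on IPX203 against 10 with any AE on IPX203 (80%). This is not decisive, since neither study's causality scale nor its cut-off is given, but it rules out treating a downward shift as established.

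A reader might also infer that expedited reporting is affected, since serious events "considered both serious and unexpected and related to the study drug are subject to expedited reporting". Protocol 12.3.2 does not say which levels count as related for that purpose, and SAP 5.1 does not govern it, so no effect is shown.

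It is also fair to say that the study is descriptive and open-label, and that no test depends on the treatment-related table. The SAP already plans all TEAEs regardless of causality, TEAEs by relationship, and listings that show causality. These limit the harm. They do not repair inconsistent coding at source, and they do not settle which rule defines the headline related count.

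**Conclusion.** The concern holds in this form: the four definitions leave a gap, the gap lies across the SAP's cut-off, and the SAP reverses the protocol's rule for Unlikely without declaring it. The first and third parts can be read directly from the text. That the gap matters in practice rests on a judgement from the population and the permitted medications, because the documents do not count such events.

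The supportable consequence is coding that may differ between sites, together with a related count that depends on which document is followed. Neither the direction nor the size of a bias can be shown. The range of 0 to 24 percentage points follows from the assumed p, g and u and is not a forecast. The point is worth acting on because the change is small and the table is a main safety output of a long-term safety study.

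**What to change.** 1. In protocol 12.2.4 and the CRF guidance, reword Possibly Related to: a logical temporal relationship such that the study medication could explain the AE, whether or not the medical condition or other therapies could also explain it. This fills the six empty cells with a logical or compelling link. State that Related takes precedence where both levels apply.
2. Assign the three remaining cells (uncertain link, no likely alternative) to a named level. The sponsor should choose. Placing them in Possibly Related would match the SAP's conservative handling of unassessed causality.
3. Reconcile SAP 5.1 with protocol 13.6, and declare any change in SAP section 7.
4. Show the related-TEAE table under both cut-offs. The difference between the two versions shows how many subjects depend on the coding of Unlikely.

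**Cost.** A few sentences of text and one extra version of a table. The related rate may rise somewhat. If data collection has started, which is likely because the SAP expects part of the study to run during the COVID-19 pandemic, AEs coded under the old and the new wording must be identifiable, including when pooled with the feeder study IPX203-B16-02. In that case the table under both cut-offs is the minimum remedy.
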